Data analysis	
 • The data will be summarized with respect to demographic, baseline characteristics, safety observations and efficacy measurements. Categorical data will be presented as frequencies and percentages. For continuous data, mean, standard deviation, median, minimum, and maximum will be presented. • The primary analysis will be based on the calculation of the observed pyrexia event rate (composite rate of grade 3/4 pyrexia, hospitalization due to pyrexia or permanent treatment discontinuation due to pyrexia) and its 95% two-sided exact confidence interval (Clopper and Pearson 1934) up to 12 months of therapy. • The study will meet its primary objective if the upper bound of the two-sided 95% CI is less than 20%. • The secondary endpoints RFS and OS distribution will be estimated by using Kaplan-Meier approach. • One IA for futility of the primary endpoint and the secondary endpoint RFS is planned for the study when approximately the first 200 subjects dosed have been followed for 6 months (either completed 6 months of treatment or discontinued treatment earlier.) • The sample size of 600 subjects has been chosen so that the study operating characteristics comply with the requirement to have a high probability (> 95%) to declare futility at IA if the true 12-month pyrexia event rate is $\geq 20\%$.
Key words	dabrafenib, trametinib, adjuvant, melanoma, combination treatment, pyrexia

Amendment 2 (12-Mar-2019)

As of 12-Mar-2019, 86 sites have been initiated, 311 subjects have enrolled into the study, and 234 subjects have started treatment in the study.

Amendment rationale

The primary purpose of this protocol amendment is to implement clinically relevant feedback received from the Health Authorities and participating center's Ethics Committees upon review of the protocol. In addition, study population inclusion criteria was expanded, clarifications and corrections are made throughout the protocol, as well as editorial change to improve flow and consistency.

Changes to the protocol

Changes to specific sections of the protocol are shown in the track changes version of the protocol using strike through red font for deletions and red underline for insertions

- Protocol Summary Section updated to match the body of the protocol
- List of Abbreviations was updated
- Section 3 - Study Design: Treatment Period was clarified:
 - One study month is equal to 4 weeks or 28 days.
- Section 5.1 - Inclusion Criteria

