12.4.2 Statistical model, hypothesis, and method of analysis

The primary analysis will be based on the calculation of the observed pyrexia event rate up to 12 months of therapy (primary endpoint) using the FAS. The observed pyrexia event rate will be summarized using descriptive statistics (N, %) along with its two-sided exact 95% confidence interval (Clopper and Pearson 1934).

In the COMBI-AD study, 87 out of 435 subjects in the treatment arm (20%) developed either grade 3/4 pyrexia or hospitalization due to pyrexia or discontinued due to pyrexia. This rate of 20% will be used as the historical control rate for the assessment of pyrexia management algorithm in this study.

Evidence of treatment effect (improvement in pyrexia event rate using the AE-management algorithm) will be concluded, if the upper bound of the two-sided 95% confidence interval is less than 20%.

The exact 95% confidence intervals for various observed event rates at the primary analysis are shown in [Table 12-1](#). If 100 (16.7%) out of 600 subjects are observed with pyrexia event, then the upper bound of the 95% confidence interval will be less than 20%.

Table 12-1 Exact 95% CI for different observed event rates at primary analysis

N	r	Pyrexia event rate (%)	95% exact CI (%)*
600	100	16.7	13.8 – 19.9
600	101	16.8	13.9 – 20.1
600	102	17.0	14.1 – 20.2
600	103	17.2	14.2 – 20.4
600	104	17.3	14.4 – 20.6
600	105	17.5	14.5 – 20.8

N: Total numbers of subjects;

r: Number of subjects with pyrexia events at primary analysis

* Clopper and Pearson (1934)

In addition, the probability that the pyrexia even rate is below the threshold of 20% will be calculated from the posterior distribution. For illustration, as shown in [Table 12-2](#), if 104 out of 600 subjects are observed with pyrexia events at primary analysis, then the posterior probability of observing an event rate of < 20% is 0.954 (probability \geq 0.95).

Table 12-2 Posterior probability for a positive effect at primary analysis

N	r	Pyrexia event rate (%)	Posterior* Pr (event rate<20% data)
600	100	16.7	0.983
600	101	16.8	0.977
600	102	17.0	0.971
600	103	17.2	0.963
600	104	17.3	0.954
600	105	17.5	0.943
600	110	18.3	0.854
600	115	19.2	0.703
600	120	20.0	0.508
600	125	20.8	0.313
600	130	21.7	0.161
600	135	22.5	0.068

N: Total numbers of subjects;

r: Number of subjects with pyrexia events at primary analysis

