12.8 Sample size calculation

The sample size calculation is based on the primary variable. The sample size of 600 has been chosen so that the study operating characteristics comply with the requirement to have a high probability (e.g. > 95%) for futility at IA if the true 12-month pyrexia event rate is > 20%, e.g., when the true pyrexia event rate is 27%, the probability is 95.5% for futility.

Operating characteristics are described below (see [Table 12-5](#)). For illustration, if the true 12-months pyrexia event rate is 30%, then there is a high chance (99.6%) of futility at the time of the IA, and the probability to continue the study and conclude success is lower than 0.001.

If the true pyrexia event rate is 20%, then the probability of observing a pyrexia event rate < 20% (i.e., study success for primary analysis) is 43.4%. If the true pyrexia event rate is lower (for example 18%), then there is 83.9% probability of declaring study success for primary analysis.

Table 12-5 Operating Characteristics

True 6 -month event rate	Probability to stop the study at IA	Probability of success at primary analysis (i.e., not stop at the IA and observe event rate < 20% at primary analysis)
16%	0.016	0.980
17%	0.040	0.939
18%	0.086	0.839
19%	0.161	0.661
20%	0.265	0.434
21%	0.391	0.228
22%	0.528	0.094
25%	0.856	0.001
26%	0.917	<0.001
27%	0.955	<0.001
28%	0.978	<0.001

True 6 -month event rate	Probability to stop the study at IA	Probability of success at primary analysis (i.e., not stop at the IA and observe event rate < 20% at primary analysis)
30%	0.996	<0.001

Probabilities are calculated based on the exact binomial distribution.

13 Ethical considerations and administrative procedures

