## 6 Sample size calculation

As per the protocol amendent version dated 09-May-2019, approximately 600 subjects were planned to be enrolled to receive dabrafenib (150 mg BID) and trametinib (2 mg once daily) combination therapy for 12 months. Due to global drug supply availability, the enrollment of patients was slower than anticipated, resulting in the final sample of 556 enrolled patients in the study by the end of anticipated recruitment period. The final sample size is reasonably close to

the planned target. The impact of the reduced sample size for the interim analyses has been discussed in detail in the Interim SAP (dated 21-Nov-2019) and DMC charter (17-Jan-2020). See Section 2.8 and Appendix B respectively for details.

The sample size calculation was based on the primary variable. The protocol amendment dated provided justification for the planned sample size of 600. However the current sample size of 556 demonstrates that the study operating characteristics comply with the requirement to have a high probability (e.g. > 95%) for futility at IA if the true 12-month pyrexia event rate is > 20%, e.g., when the true pyrexia event rate is 27%, the probability is 95.5% for futility at interim analysis.

Detailed Operating characteristics are described below (see [Table 2-8](#)). For illustration, if the true 12-months pyrexia event rate is 30%, then there is a high chance (99.6%) of futility at the time of the interim, and the probability to continue the study and conclude success is lower than 0.001.

If the true pyrexia event rate is 20%, then the probability of observing a pyrexia event rate < 20% (i.e., study success for primary analysis) is 46.3%. If the true pyrexia event rate is lower (for example 18%), then there is 84.6% probability of declaring study success for primary analysis.

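### The stated success probabilities at a true rate of 18% (83.9% and 84.6%) use a looser criterion than the plan's own success rule, under which they are about 21% and 20%

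*Protocol*

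**What the plan says.** The success rule is the same wherever it is given. The protocol summary states: "The study will meet its primary objective if the upper bound of the two-sided 95% CI is less than 20" per cent. Protocol section 12.4.2 says that evidence of an effect "will be concluded, if the upper bound of the two-sided 95% confidence interval is less than 20" per cent, with the interval being Clopper-Pearson, and SAP section 5.5.2 repeats this. The 20% is the COMBI-AD rate (87 of 435). Protocol Table 12-1 and SAP Table 2-5 turn the rule into counts: 100/600 passes (upper limit 19.9%) and 101/600 fails (20.1%); 92/556 passes (19.9%) and 93/556 fails (20.1%).

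The sample size sections define success differently. The last column of protocol Table 12-5 and SAP Table 2-8 is headed as the probability of success, and it counts trials that pass the interim and observe a rate below 20%. The text then treats this as the trial's success criterion. For a true rate of 18% the protocol says "then there is 83.9% probability of declaring study success for primary analysis" and the SAP says "then there is 84.6% probability of declaring study success for primary analysis". For a true rate of 20% they print 43.4% and 46.3%.

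**The concern.** An observed rate below 20% and an upper confidence limit below 20% are very different hurdles. The first is met by 119/600 (19.8%) or 111/556 (20.0% after rounding, 19.96% exactly). The second needs 16.7% or 16.5% or less. Every count from 101 to 119 (N=600), or from 93 to 111 (N=556), is a success in the operating-characteristics tables and a failure in the primary analysis. Protocol Table 12-1 itself lists one such case: 105/600, with an interval reaching 20.8%.

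These are the only prospective success probabilities in either document. A reader would conclude that the trial is well powered for a fall from 20% to 18%, and would judge a negative result against a claimed chance of success of about 84%. The reader would also see a 43% to 46% chance of success for an algorithm that does nothing, which makes the design look far more prone to a false positive than it is.

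**Working it through.** **Inputs**
- N = 600 (protocol 12.8) and N = 556 (SAP section 6).
- Interim after 200 subjects (protocol 12.7).
- Interim stop at 44 or more events in 200. This is inferred: protocol 12.7 illustrates possible stopping at an observed 22%, where Table 12-3 gives a predictive probability of 0.8058. The printed stop column confirms it (next step).
- Exact binomial probabilities, as the footnotes to both tables say.
- One true rate p applied to both the interim and the primary analysis.

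**Interim check.** P(X ≥ 44), with X ~ Bin(200, p), is 0.016, 0.040, 0.086, 0.161 and 0.265 (0.2645 before rounding) for p = 16% to 20%. These match the printed stop column.

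**Formula.** With c the largest event count that still counts as success,

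P(success) = Σ over x = 0 to 43 of P(Bin(200, p) = x) × P(Bin(N − 200, p) ≤ c − x).

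**Step 1: reproduce the printed columns.** An observed rate below 20% means c = 119 for N = 600 (20% of 600 is 120) and c = 111 for N = 556 (20% of 556 is 111.2). At p = 18% this gives 0.8389 and 0.8459; at p = 20%, 0.4341 and 0.4633. All rows from 16% to 20% agree with the tables to within 0.001, so this is how the tables were built.

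**Step 2: find c under the plan's rule.** The Clopper-Pearson upper limit is the 97.5% quantile of Beta(r + 1, N − r).
- N = 600: r = 100 gives 19.89%; r = 101 gives 20.07%. So c = 100.
- N = 556: r = 92 gives 19.90%; r = 93 gives 20.09%. So c = 92.

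These agree with protocol Table 12-1 and SAP Table 2-5.

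**Step 3: change only c.**

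| True rate | N=600 printed | N=600 plan's rule | N=556 printed | N=556 plan's rule |
|---|---|---|---|---|
| 16% | 0.980 | 0.693 | 0.980 | 0.662 |
| 17% | 0.939 | 0.438 | 0.940 | 0.413 |
| 18% | 0.839 | 0.213 | 0.846 | 0.202 |
| 19% | 0.661 | 0.078 | 0.679 | 0.076 |
| 20% | 0.434 | 0.021 | 0.463 | 0.022 |

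**Step 4: rate giving 80% power.** Solving P(success) = 0.80 gives p = 15.50% for N = 600 and p = 15.35% for N = 556. At p = 15% the power is 0.883 and 0.859.

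**Sensitivity**
- Dropping the interim altogether gives 0.214 (N=600) and 0.202 (N=556) at 18%, and 0.022 for both sizes at 20%. The inferred boundary hardly matters.
- Both documents also report a posterior probability, illustrated at 0.95 or more (104/600, 96/556). Using those cut-offs as the success rule gives only 0.355 and 0.347 at 18%, so that criterion does not explain the printed figures either.

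**The case against.** The strongest points on the other side are these.

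- **The column header discloses its criterion, and the numbers are right for it.** This stands: nothing is miscalculated. The fault is that two definitions of success are in use. But the header still calls the result the probability of success, the text speaks of declaring study success, and neither warns that section 12.4.2 applies a different rule.
- **The sample size was justified by futility, not power.** This also stands. The stated requirement is a high probability of futility at the interim, for example 95.5% at a true rate of 27%. That comes from the stop column, which is correct and does not depend on the final N. No power target is given. The success probabilities are nevertheless offered as properties of the design, and they are wrong under its own rule.
- **The primary inference is unaffected.** True. The decision rule is clear, its cut-offs are tabulated, and its false-positive rate is about 2%.
- **Nothing shows that the data monitoring committee relied on this table.** Agreed. Protocol 12.7 has it receive predictive probabilities, and no claim is made here about what it was told.
- **The SAP is a final-analysis version, with the interim done and recruitment closed at 556.** A corrected SAP table can no longer inform the design. It still matters for the record and for anything in the study report taken from it, since the SAP recalculated this column for 556 and kept the same criterion.

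**Conclusion.** The concern holds. Under the plan's own rule the probability of success at a true rate of 18% is 21.3% (N=600) or 20.2% (N=556), not 83.9% or 84.6%: an overstatement of about 63 and 64 percentage points. At a true rate of 20% it is 2.1% or 2.2%, not 43.4% or 46.3%. The printed column therefore overstates power and, at the null, misrepresents the false-positive risk as roughly twenty times what it is (0.434 / 0.021 and 0.463 / 0.022 are both about 21).

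The figures assume an interim stop at 44/200, treated as binding although the protocol presents it only as an illustration, and one event rate at both analyses. The second assumption needs stating because both tables label the rate as 6-month while the text calls it 12-month. Removing the interim moves the 18% and 20% results by no more than 0.001.

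**What to change.** 1. Recompute the last column of protocol Table 12-5 and SAP Table 2-8 with success defined as a Clopper-Pearson upper limit below 20% (at most 100/600; at most 92/556), and reword the column header to match.
2. In the text, replace 83.9% and 84.6% by 21.3% and 20.2%, and 43.4% and 46.3% by 2.1% and 2.2%. Remove the wording that equates an observed rate below 20% with study success.
3. State the true rate at which the trial has 80% power: about 15.5% for N=600 and 15.4% (15.35%) for N=556.
4. State the interim boundary used in the calculation, and settle whether the tabulated rate is at 6 or 12 months.
5. If the study report takes over either table, use the corrected figures.

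The cost is a correction to text and tables, and a less favourable stated power. It needs no further subjects, no new data and no change to the analysis. If the probability of observing a rate below 20% is still wanted, it can stay as a separate column under that name.

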13.1 Regulatory and ethical compliance

This clinical study was designed and shall be implemented, executed and reported in accordance with the ICH Harmonized Tripartite Guidelines for Good Clinical Practice, with applicable local regulations (including European Directive 2001/20/EC, US CFR 21), and with the ethical principles laid down in the Declaration of Helsinki.

13.2 Responsibilities of the investigator and IRB/IEC

Before initiating a trial, the investigator/institution must obtain approval/favorable opinion from the Institutional Review Board/Independent Ethics Committee (IRB/IEC) for the trial protocol, written informed consent form, consent form updates, subject recruitment procedures (e.g., advertisements) and any other written information to be provided to subjects. Prior to study start, the investigator is required to sign a protocol signature page confirming his/her agreement to conduct the study in accordance with these documents and all of the instructions and procedures found in this protocol and to give access to all relevant data and records to Novartis monitors, auditors, Novartis Quality Assurance representatives, designated agents of Novartis, IRBs/IECs, and regulatory authorities as required. If an inspection of the clinical site is requested by a regulatory authority, the investigator must inform Novartis immediately that this request has been made.

13.3 Publication of study protocol and results

The protocol will be registered in a publicly accessible database such as clinicaltrials.gov and as required in EudraCT. In addition, after study completion (defined as last patient last visit) and finalization of the study report the results of this trial will be submitted for publication and posted in a publicly accessible database of clinical trial results, such as the Novartis clinical trial results website and all required Health Authority websites (e.g. Clinicaltrials.gov, EudraCT etc.).

For details on the Novartis publication policy including authorship criteria, please refer to the Novartis publication policy training materials that were provided to you at the trial investigator meetings

13.4 Quality Control and Quality Assurance

Novartis maintains a robust Quality Management System (QMS) that includes all activities involved in quality assurance and quality control, to ensure compliance with written Standard Operating Procedures as well as applicable global/local GCP regulations and ICH Guidelines.

Audits of investigator sites, vendors, and Novartis systems are performed by auditors, independent from those involved in conducting, monitoring or performing quality control of the clinical trial. The clinical audit process uses a knowledge/risk based approach.

Audits are conducted to assess GCP compliance with global and local regulatory requirements, protocols and internal SOPs, and are performed according to written Novartis processes

14 Protocol adherence

This protocol defines the study objectives, the study procedures and the data to be collected on study participants. Additional assessments required to ensure safety of subjects should be administered as deemed necessary on a case-by-case basis. Under no circumstances including incidental collection is an investigator allowed to collect additional data or conduct any additional procedures for any purpose involving any investigational drugs under the protocol, other than the purpose of the study. If despite this interdiction prohibition, data, information, observation would be incidentally collected, the investigator shall immediately disclose it to Novartis and not use it for any purpose other than the study, except for the appropriate monitoring on study participants.

Investigators ascertain they will apply due diligence to avoid protocol deviations. If an investigator feels a protocol deviation would improve the conduct of the study this must be considered a protocol amendment, and unless such an amendment is agreed upon by Novartis and approved by the IRB/IEC and health authorities, where required, it cannot be implemented.

16.1 Appendix 1: AJCC Melanoma Staging Eight Edition

Table 16-1 Melanoma Stage III Subgroups Based on Primary Tumor (T) and Regional Lymph Nodes (N) categories

AJCC Eighth Edition Melanoma Stage III Subgroups									
N Category	T Category								
	T0	T1a	T1b	T2a	T2b	T3a	T3b	T4a	T4b
N1a	N/A	A	A	A	B	B	C	C	C
N1b	B	B	B	B	B	B	C	C	C
N1c	B	B	B	B	B	B	C	C	C
N2a	N/A	A	A	A	B	B	C	C	C
N2b	C	B	B	B	B	B	C	C	C
N2c	C	C	C	C	C	C	C	C	C
N3a	N/A	C	C	C	C	C	C	C	D
N3b	C	C	C	C	C	C	C	C	D
N3c	C	C	C	C	C	C	C	C	D

Instructions
 
(1) Select patient's N category at left of chart. (2) Select patient's T category at top of chart. (3) Note letter at the intersection of T&N on grid. (4) Determine patient's AJCC stage using legend.
 
N/A=Not assigned
	
Legend
 
 
 A	Stage IIIA	
 
 B	Stage IIIB	
 
 C	Stage IIIC	
 
 D	Stage IIID	
 
	A	Stage IIIA	B	Stage IIIB	C	Stage IIIC	D	Stage IIID
A	Stage IIIA								
B	Stage IIIB								
C	Stage IIIC								
D	Stage IIID								

Table 16-2 Definition of Regional Lymph Node (N)

EXTENT OF REGIONAL LYMPH NODE AND/OR LYMPHATIC METASTASIS		
N CATEGORY	NO. OF TUMOR-INVOLVED REGIONAL LYMPH NODES	PRESENCE OF IN-TRANSIT, SATELLITE, AND/OR MICROSATELLITE METASTASES
NX	Regional nodes not assessed (eg, sentinel lymph node [SLN] biopsy not performed, regional nodes previously removed for another reason); Exception: pathological N category is not required for T1 melanomas, use clinical N information	No
N0	No regional metastases detected	No
N1	One tumor-involved node or any number of in-transit, satellite, and/or microsatellite metastases with no tumor-involved nodes	
N1a	One clinically occult (ie, detected by SLN biopsy)	No
N1b	One clinically detected	No
N1c	No regional lymph node disease	Yes
N2	Two or 3 tumor-involved nodes or any number of in-transit, satellite, and/or microsatellite metastases with one tumor-involved node	
N2a	Two or 3 clinically occult (ie, detected by SLN biopsy)	No
N2b	Two or 3, at least one of which was clinically detected	No
N2c	One clinically occult or clinically detected	Yes
N3	Four or more tumor-involved nodes or any number of in-transit, satellite, and/or microsatellite metastases with 2 or more tumor-involved nodes, or any number of matted nodes without or with in-transit, satellite, and/or microsatellite metastases	
N3a	Four or more clinically occult (ie, detected by SLN biopsy)	No
N3b	Four or more, at least one of which was clinically detected, or the presence of any number of matted nodes	No
N3c	Two or more clinically occult or clinically detected and/or presence of any number of matted nodes	Yes

Reproduced from Amin MB, Edge SB, Greene FL, et al, eds. AJCC Cancer Staging Manual. 8th ed. New York: Springer; 2017.

**Document History – Changes compared to previous final version of SAP**

Date	Time point	Reason for update	Outcome for update	Section and title impacted (Current)
	Prior to database lock	Incorporate changes as per protocol amendment 1 and 2	First version	NA
22 September 2020	Prior to database lock of primary analysis	Addition of analyses to describe and adjust for impact of COVID-19	Additional outputs added for analysis to describe and adjust for impact of COVID-19	
22 September 2020	Prior to database lock of primary analysis	Addition of analyses to support the pyrexia label update	Addition of analyses to support the pyrexia label update	
20 July 2021	Prior to the final database lock	Final output specifications		

